3. STUDY DESIGN

3.1 DESCRIPTION OF THE STUDY

This is a multicenter, prospective, open-label Phase IV clinical trial. Patients with relapsing forms of MS, ages 18 to 65, who have received a stable dose of NTZ for 12 or more consecutive months, and have been free of relapses, disability worsening or MRI progression 6 months prior to the transition screening visit will be eligible for the study. After informed consent to participate has been obtained, the patient will have a neurological exam, EDSS, 3T or 1.5T MRI, MSIS-29 and labs done for the screening visit to determine eligibility. 3T or 1.5T brain MRI with and without contrast will be performed with the standard MS protocol. It is preferred that the MRIs are done on a 3T scanner for this trial, but not required. MRIs will be performed with 3mm slice thickness with no gaps between slices. Patients will receive their first dose of OCR 4 to 6 weeks after the last dose of NTZ. Other baseline measures, including EDSS, MSIS-29, and labs will be performed within 4 weeks of screening. A neurological exam, EDSS, and labs will be performed at month 3, month 6, month 9, and month 12. MSIS-29 will be performed at months 6 and 12. MRIs will be performed at screening to determine

eligibility and at months 3, 6, and 12. All adverse events will be reported to the study sponsor. OCR will not be provided by the study; the medication will be supplied through the patient's commercial pharmacy and billed to the patient or the patient's insurance.

Patients will receive OCR 4-6 weeks after their last infusion of NTZ. OCR 300mg IV will be given on Day 0 and repeated with the same dose on Day 14±2. Patients will then receive OCR 600mg IV every 24 weeks.

If discontinuation of study drug occurs, the subject may continue in the trial for observational purposes. If willing to continue, they will complete all visit items moving forward, with the exception of study drug dosing and pregnancy testing (if applicable). If study drug is discontinued and the subject is unwilling to continue in the trial, a premature termination visit will be completed as soon as possible.

The target enrollment is 50 patients from 5 centers. Serious adverse events recorded during the trial will be reported to the study sponsor via Medwatch form.

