3.3.2 Secondary Outcome Measures

- Proportion of relapse free patients at months 3, 6, and 9
- Annualized Relapse Rate (ARR)
- Mean time to first relapse on OCR
- Proportion of patients free from MRI evidence of MS disease activity at months 3, 6, and 12
- Proportion of patients with new or enlarging T2 lesions at 3, 6, and 12 months. For patients with new or enlarging lesions, the number of new and enlarging lesions
- Proportion of patients with new Gd+ lesions at months 3, 6, and 12. For patients with new Gd+ lesions, number of new Gd+ lesions detected at months 3, 6, and 12.
- Change in the EDSS score from baseline to month 12.
- Change in MSIS-29 from baseline to months 6 and 12
- Number and type of AEs and SAEs
- Proportion of patients that discontinued OCR

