4.1.3 Exclusion Criteria

1. History of primary or secondary progressive multiple sclerosis.
2. Evidence of active hepatitis B infection at screening.
3. Any mental condition of such that patient is unable to understand the nature, scope, and possible consequences of the study.
4. Patients with untreated hepatitis C or tuberculosis. Patients who have history of PML or known to be HIV positive, per standard care.
5. Any persistent or severe infection.
6. Pregnancy or lactation.

7. Significant, uncontrolled somatic disease or severe depression in the last year.
8. Inability to complete an MRI.
9. Previous treatment with B-cell targeted therapies.
10. Current use of immunosuppressive medication.
11. Patients who have had evidence of disease activity within the 6 months prior to screening. This includes MS relapse, or new or enlarging T2 lesions or Gd+ enhancing lesions, or disability progression.
12. Patients with any significant comorbidity that in the opinion of the investigator, would interfere with participation in the study.

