4.9 STATISTICAL METHODS

4.9.1 Analysis of the Conduct of the Study

The following documentation will be collected and analyzed for all enrolled patients in order to maintain the integrity of the study:

- A. Enrollment date and time
- B. Demographic information
- C. Baseline disease status
- D. If applicable, protocol violation date and cause
- E. If applicable, discontinuation date and cause

Demographic information and baseline disease for all enrolled patients, those who violated protocol, and those who discontinued will be summarized and reported separately. The reasons for discontinuing or violating protocol and the patient's time on drug at occurrence will be reported and any influence on the trial results will be discussed. To assess the comparability between centers, summaries will be reported for all patients overall and by study center. Any other irregularities that result in missing data will be fully identified and discussed.

All patients that followed protocol will be used to evaluate efficacy, safety, and tolerability. This includes patients that discontinued but followed protocol up to discontinuation.

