4.9.3 Efficacy Analysis

a. Primary Endpoint

Proportion of patients relapse free at 12 months after switching from NTZ to OCR

b. Secondary Endpoints

- Proportion of patients relapse-free at 3, 6, and 9 months after switching to OCR
- Mean time to first relapse
- MRI evidence of MS disease activity
- Proportion of patients with New or Enlarging T2 lesions at 3, 6, and 12 months. For patients with New or Enlarging T2 lesions, number of New and Enlarging T2 lesions.
- Proportion of patients with New Gd+ lesions detected at months 3, 6, and 12. For patients with New Gd+ lesions, number of New Gd+ lesions
- Annualized relapse rate (ARR)
- Change in EDSS from baseline to 12 months
- Change in MSIS-29 from baseline to 6 and 12 months

All patients that followed protocol will be used to evaluate the proportion of patients relapse-free at 3, 6, 9, and 12 months, mean time to first relapse, and ARR. This includes those that discontinued early but followed protocol up to discontinuation. All patients that followed protocol and did not discontinue will be used to evaluate MRI

evidence of MS disease activity at 3, 6, and 12 months, the change in MSIS-29 from baseline to 6 and 12 months, and the change in EDSS from baseline to 12 months.

A full analysis set consistent with the intent-to-treat (ITT) principle will also be used to analyze the proportion of patients relapse-free at 3, 6, 9, and 12 months, mean time to first relapse, and ARR using all subjects. Subjects who entered the trial and did not meet inclusion criteria may be excluded.

Summary statistics will be presented for continuous variables (mean, standard deviation, median, range) and categorical variables (counts and percentages). All analyses will use two-sided confidence intervals and p-values at the 0.05 significance level.

Primary Analysis

Kaplan-Meier survival analysis methodology will be used to determine the proportion of patients relapse-free at months 3, 6, 9, and 12. Median and mean time to first relapse with confidence intervals will be reported. Log rank tests and graphical presentations of Kaplan Meier curves with confidence intervals will be used to examine effects of center, gender, categorized age, categorized EDSS and duration of disease on survival distribution.

Secondary Analysis

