4.9.5 Missing Data

Demographic information and baseline disease for patients who followed protocol and completed the study, violated protocol, and discontinued the study will be reported separately and compared. The reasons for discontinuing or violating protocol and the patient's time on drug at occurrence will be reported and any influence on the trial results will be discussed. To assess the comparability between centers, summaries will be reported for all patients overall and by study center. Any other irregularities that result in missing data will be fully identified and discussed.

For the per protocol and full analysis sets, missing data due to discontinuation will be incorporated as censored time points in the survival analysis of relapse-free patients and ARR will be calculated using the range of time that the individual was in the study. If interim time points at 3, 6, or 9 months are missing, only the time points available will be used in the survival analysis. No relapse data will be missing at baseline, since only patients relapse free for six months are included. For the Kaplan Meier analyses and

log rank tests stratified by age, gender, EDSS, and center, we expect these patient characteristics to be non-missing. However, if they are missing, a complete case analysis per variable will be used and the number of missing will be reported.

For the analysis of the change in EDSS and MSIS-29, a complete case analysis with per protocol patients will be used.

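### MRI and MSIS-29 values already obtained are excluded when the patient later discontinues, with no full-analysis-set version, and other parts of Section 4.9 conflict with this rule or leave it unclear

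*Combined protocol and SAP*

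**What the plan says.** Section 4.9.3 sets two populations. Relapse-free proportions, time to first relapse and ARR use patients who followed the protocol, including those who stopped early. For the remaining outcomes it says "All patients that followed protocol and did not discontinue will be used to evaluate MRI" disease activity at months 3, 6 and 12; the same sentence covers MSIS-29 change at months 6 and 12 and EDSS change at month 12.

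A wider population is then added: "A full analysis set consistent with the intent-to-treat (ITT) principle will also be used to analyze the proportion of patients relapse-free". The list goes on to time to first relapse and ARR and ends there. MRI, EDSS and MSIS-29 are not on it.

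Three other places bear on the same question:

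- Section 4.9.1 gives a general rule for the efficacy set: "This includes patients that discontinued but followed protocol up to discontinuation".
- Section 4.9.5 says "For the analysis of the change in EDSS and MSIS-29, a complete case analysis with per protocol patients will be used". The same section treats discontinuation in the per-protocol set as a censored time, so that set contains discontinuers.
- Section 3.1 allows a patient who stops the drug to stay for observation: "If willing to continue, they will complete all visit items moving forward", apart from dosing and pregnancy testing.

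**The concern.** A scan taken at month 3 is a valid month-3 observation whatever the patient does at month 7. Excluding it because of a later event is not a missing-data problem: the value was obtained and then set aside. In a single-arm trial no comparator shares the selection, so any link between leaving and disease activity goes straight into the reported proportion.

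Such a link is possible. Appendix A, note M, has the investigator review the month-6 MRI before the month-6 infusion, and Section 4.6 lets a patient stop for any reason.

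The affected endpoints are secondary, and the primary relapse-free endpoint is untouched. But the primary objective in Section 2.1 names MRI and disability progression next to relapse, so these results carry part of the trial's stated purpose. MSIS-29 belongs to a secondary objective (Section 2.2).

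**Working it through.** **1. What each passage does with a discontinuer's earlier value**

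| Place | Discontinuer's month-3 or month-6 value |
|---|---|
| 4.9.3, sentence on MRI, MSIS-29 and EDSS | Excluded |
| 4.9.3, full analysis set | Not covered (relapse outcomes only) |
| 4.9.1, general efficacy set | Kept |
| 4.9.5, complete-case rule | Month-6 MSIS-29 kept, if the per-protocol set includes discontinuers as its censoring rule implies; no rule for MRI |
| 4.9.3, Secondary Analysis, lesion counts | No population named |

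Section 4.9.5 therefore conflicts with Section 4.9.3 on MSIS-29 and does not repeat its rule.

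**2. Drug or study?** The documents use both senses. Section 3.3.2 has "Proportion of patients that discontinued OCR" (drug). Section 4.9.5 says that patients who completed, "violated protocol, and discontinued the study will be reported separately and compared" (study).

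- *Study reading.* A leaver has no scheduled month-12 value. The premature termination visit collects EDSS and MSIS-29 but no MRI. Nothing scheduled at month 12 is dropped.
- *Drug reading.* Month-12 MRI, EDSS and MSIS-29 from patients who stop OCR and stay for observation are collected and then excluded. The documents give no number for such patients.

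Earlier scans and scores are lost under either reading.

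**3. How many patients?** Section 4.9.6 assumes 45 evaluable patients and 10% attrition: 45/0.90 = 50, as stated, so 5 leavers. (The 45 is also close to what a two-sided Wald limit gives: 1.96² × 0.80 × 0.20 / (0.80 − 0.68)² = 42.7, so 43.) For a low case, Section 3.2 cites withdrawals for side effects of 3.2% and 3.8%: 0.032 × 50 = 1.6 and 0.038 × 50 = 1.9, so about 2.

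**4. Size at month 6.** Assumptions, not from the documents: 2 of 45 completers are active; 3 of the 5 leavers go after their month-6 scan; 0 to 3 of those 3 were active; nobody is excluded for a protocol violation.

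- Reported: 2/45 = 4.4%, exact 95% interval 0.5% to 15.1%.
- All scanned patients: 2/48 = 4.2%, 3/48 = 6.3%, 4/48 = 8.3%, 5/48 = 10.4%.

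The whole range lies inside the interval for 2/45.

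**5. Size at month 3.** Assumptions: 5% activity in completers, and p = 0, 20, 40 or 60% in leavers. The reported figure is 5.0% throughout.

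- 5 leavers, all scanned, (45 × 0.05 + 5p)/50: 4.5%, 6.5%, 8.5%, 10.5%.
- 5 leavers, 3 scanned, (45 × 0.05 + 3p)/48: 4.7%, 5.9%, 7.2%, 8.4%.
- 2 leavers, both scanned, (48 × 0.05 + 2p)/50: 4.8%, 5.6%, 6.4%, 7.2%.

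The plan gives no expected number of protocol violators, so that loss is not sized.

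**The case against.** The strongest reply is that one sentence in Section 4.9.3 stands against two sections that keep discontinuers, so the data may never be dropped. This stands in part: for MSIS-29 the plan contradicts itself and does not give one clear exclusion. It does not settle MRI. There Section 4.9.5 is silent, and the sentence in 4.9.3 is the endpoint-specific rule, placed directly after a relapse rule that expressly keeps early discontinuers.

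The numbers are small, and the larger shifts need leavers to be far more active than completers. That stands. It also stands that no outcome-dependent mechanism is shown: the mandatory stopping list in Section 4.6 does not name MRI activity, and note M requires only a review.

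Sections 4.9.1 and 4.9.5 promise to report reasons for discontinuation and time on drug, and to discuss any influence on the results. This makes the exclusion visible but does not restore the values.

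Three stronger readings are tempting and are not supported:

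- *The T2 and Gd+ endpoints are certainly under the same rule.* A reader might infer this from exclusion 11, which says of disease activity "This includes MS relapse, or new or enlarging T2 lesions or Gd+ enhancing lesions, or disability progression". That is an eligibility criterion, not an analysis set. The protocol lists these endpoints separately from MRI disease activity, and the restricted sentence does not name them. Their set is unclear.
- *Up to 5 month-12 values are lost under the drug reading.* The 10% attrition allowance does not give this count: patients who stay for observation need not be attrition, and patients who leave have no scheduled month-12 value.
- *The rule makes OCR look better.* The direction is unknown; if leavers are less active than completers, the reported figure is too high.

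**Conclusion.** The point holds, as a should-fix on secondary endpoints. Certain from the text: the rule in Section 4.9.3 excludes values already obtained because of a later event, the full analysis set omits MRI, EDSS and MSIS-29, and Sections 4.9.1 and 4.9.5 do not agree with that rule. Open: what *discontinue* means, which population the T2 and Gd+ endpoints use, and how many month-12 values are at risk.

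With 2 to 5 discontinuers the effect is a few patients, from a small fall to a rise of about 6 percentage points in the month-6 illustration (4.4% to between 4.2% and 10.4%). That rests wholly on assumed activity rates and exit times. Lying within sampling error means that the trial could not detect the distortion; it does not justify a selection that can be avoided at no data cost.

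**What to change.** 1. At each scheduled visit, analyse every OCR-treated patient with a scan at that visit, for the composite MRI, T2 and Gd+ endpoints alike. For EDSS and MSIS-29, analyse every treated patient with a baseline and a visit value. Do this whatever happens later, and include patients who stopped OCR but stayed for observation. Report premature-termination values separately.
2. Keep the completers-only per-protocol analysis as a sensitivity analysis.
3. State whether *discontinue* means the drug or the study, and align Sections 4.9.1, 4.9.3 (including its Secondary Analysis paragraph) and 4.9.5.
4. Report the number analysed at each visit.

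Cost: an amendment to Section 4.9, with approval by the Providence IRB and each site's IRB or Ethics Committee (Section 3.5), and revised tables. Denominators will differ by visit, and estimates may move either way. No visits or scans are added. Patients who leave before a scan still cannot be recovered, because the premature termination visit has no MRI.

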Ocrelizumab (OCR), a humanized monoclonal antibody that selectively binds to, and destroys CD20-expressing lymphocytes (B-cell lymphocytes), has demonstrated robust efficacy in reducing relapse rate with a relative reduction of 46% and 47% respectively in OPERA I and II^{xi}. In addition, OCR treatment compared to interferon-β1a therapy led to a significant reduction in contrast enhancing lesions on MRI especially at 24 weeks, 48 weeks, and 96 weeks of treatment with a relative reduction of 94% and 95% respectively. Disability progression at 12 and 24 weeks were also significantly different between both groups with a relative reduction of 40% at 96 weeks. No evidence of disease activity (NEDA) was present in 48% of patients at 96 weeks. The percentage of patients meeting NEDA in the AFFIRM trial was only 37%^{xii}. Also, the number was more impressive for OCR with 72% of patients meeting NEDA when assessed after 24 weeks^{xiii}.

In OPERA I and II, adverse events were the same between the two groups. Not surprisingly, infusion related reactions were more common with 11 patients stopping OCR. Also, in patients receiving OCR, upper respiratory infections and nasopharyngitis were more common. However, unlike NTZ, OCR use has not been associated with the risk of developing PML in patients with MS. Also, to date, there are no reported cases of PML in patients who have received rituximab for the treatment of MS.

The robust therapeutic efficacy of OCR in the phase III pivotal trials, the absence of evidence of PML risk, and the convenience of fewer infusions, makes it an attractive alternative therapy for patients with MS being treated with NTZ, particularly those with the presence of anti-JCV antibodies. However, patients who are JCV negative will likely also be interested in OCR given the potential risk of a false negative to the JCV virus with the reported rate of sero-conversion at 2 to 3 percent per year^{xiv}.

Given the efficacy and safety data demonstrated in these trials, OPERA I and II, we anticipate that physicians and patients with relapsing MS being treated with NTZ independent of the JCV status would be interested in transitioning to OCR.

However, breakthrough disease is well documented in patients electively coming off NTZ to reduce PML risk. Therefore, conducting a study to determine if patients on NTZ regardless of their JCV status can be transitioned to OCR safely without disease progression is vital.

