2. OBJECTIVES

2.1 PRIMARY OBJECTIVES

The primary objective of this study is to assess the efficacy of OCR in RMS patients who have been previously treated with NTZ by evaluating relapse rate, progression on MRI and disability progression.

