3.3 OUTCOME MEASURES

3.3.1 Primary Outcome Measure

The primary endpoint is the proportion of relapse-free patients at month 12 after switching from NTZ to OCR.

Relapse is defined as:

Protocol: Ocrelizumab Providence Health & Services

Page 5 of 34 ML39655

- Occurrence of new or worsening neurological symptoms attributable to MS
- Symptoms persisting for > 24 hours
- Symptoms not attributable to confounding clinical factors (e.g., fever, infection, injury, adverse reaction to medication)
- Symptoms immediately preceded by a stable or improving neurological state for at least 30 days
- Symptoms accompanied by objective neurological worsening consistent with an increase of at least half a step on the EDSS scale, or 2 points on one of the appropriate FSS, or 1 point on 2 or more of the appropriate FSS; the change has to affect the selected FSS (i.e. pyramidal, ambulation, cerebellar, brainstem, sensory, or visual)

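### MRI and EDSS results exclude patients who discontinue while relapse results include them, so the proportion staying free of relapse, MRI activity and disability worsening cannot be recovered from the planned analyses

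*Combined protocol and SAP*

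**What the plan says.** Section 2.1 sets out to assess efficacy "by evaluating relapse rate, progression on MRI and disability progression". The introduction says that finding out whether patients "can be transitioned to OCR safely without disease progression is vital". Exclusion criterion 11 in section 4.1.3 bars anyone with a relapse, new MRI activity or disability progression in the six months before screening, so every patient should enter free of all three.

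The outcomes treat the domains separately:

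- **Relapse.** Section 3.3.1: "The primary endpoint is the proportion of relapse-free patients at month 12 after switching from NTZ to OCR". Section 4.9.3 analyses it by Kaplan-Meier in protocol followers, including those who discontinued early, and again in a full analysis set. Section 4.9.5 censors at discontinuation.
- **MRI.** Section 3.3.2: "Proportion of patients free from MRI evidence of MS disease activity at months 3, 6, and 12". Section 4.9.3 restricts the set: "All patients that followed protocol and did not discontinue will be used to evaluate MRI" activity.
- **Disability.** Section 3.3.2: "Change in the EDSS score from baseline to month 12". Section 4.9.3 applies the same restriction as for MRI and reports mean and median change with a Wilcoxon signed-rank test. Section 4.9.5 makes this a complete-case analysis. No worsening threshold is defined.

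Section 4.9.1, by contrast, says that protocol followers who discontinued count in the evaluation of efficacy. Section 3.1 lets patients who stop ocrelizumab stay under observation with nearly all visit items continued.

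**The concern.** Two consequences follow from the way section 4.9.3 is built.

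First, MRI and EDSS findings from patients who stop are collected but not analysed for efficacy. Section 4.9.3 does not say whether discontinuing means stopping ocrelizumab or leaving the study. On the first meaning, patients kept under observation under section 3.1 are dropped. On either meaning, scans and EDSS scores obtained before a patient left the study are dropped. If patients with active disease are more likely to stop, the MRI and EDSS results will look better than the cohort did.

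Second, the trial selects patients free of all three kinds of activity but never reports how many remain so. A patient with new lesions or EDSS worsening and no protocol-defined relapse counts as a success on the headline endpoint. If the combined figure is built after the data are seen, its EDSS rule, patient set and handling of leavers will all be chosen with the results in view.

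**Working it through.** **1. The plan's own figure.** Section 4.9.6 assumes 0.80 relapse-free, 45 evaluable patients and a 95% lower limit of 0.68.

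- Normal-approximation lower limit: 0.80 − 1.96 × √(0.80 × 0.20 / 45) = 0.683.
- Patients needed for a half-width of 0.12: 1.96² × 0.16 / 0.12² = 42.7, so 43, which is close to 45.
- With 10% attrition: 45 / 0.90 = 50.

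The sample size reproduces on this basis and is not in dispute.

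**2. Separate proportions in one common set.** For proportions a, b and c in the same patients, the joint proportion lies between max(0, a + b + c − 2) and min(a, b, c). Only a = 0.80 comes from the plan. The MRI-free and EDSS-worsening-free values are assumptions.

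| Relapse-free | MRI-free (assumed) | EDSS-free (assumed) | Lowest joint | Independence | Highest joint |
|---|---|---|---|---|---|
| 0.80 | 0.85 | 0.90 | 0.55 | 0.612 | 0.80 |
| 0.80 | 0.95 | 0.95 | 0.70 | 0.722 | 0.80 |
| 0.80 | 0.70 | 0.85 | 0.35 | 0.476 | 0.70 |

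For the first row: 0.80 + 0.85 + 0.90 − 2 = 0.55, and 0.80 × 0.85 × 0.90 = 0.612. The width is 10 to 35 points across these rows. If all three proportions are high (0.95, 0.90, 0.95, all assumed), the range is 0.80 to 0.90.

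**3. Effect of the different sets.** Suppose that 40 of 50 patients are relapse-free, 5 of the 50 discontinue, and among the 45 who do not, 41 are MRI-free and 41 free of EDSS worsening. All these counts are assumed; simple counts stand in for the Kaplan-Meier estimate.

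- Relapse-free among the 45: from 40 − 5 = 35 (all five who stopped were relapse-free) to 40 (none was).
- Lowest joint count: 35 + 41 + 41 − 2 × 45 = 27, and 27/45 = 0.60.
- Highest joint count: min(40, 41, 41) = 40, and 40/45 = 0.89.

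The joint figure among non-discontinuers can thus exceed the 40/50 = 0.80 reported for relapse in the larger set.

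**4. Are the inputs planned outputs?** The relapse-free proportion is. The MRI-free proportion is planned by visit, with no cumulative 12-month status stated. The proportion free of EDSS worsening is not planned at all. A mean or median change near zero is compatible with some patients worsening while others improve, so even the bounds in step 2 cannot in general be formed from the planned tables.

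**The case against.** The strongest reply is that nothing was promised and nothing is broken. The objective lists three things to evaluate, and each has an outcome. The combined measure appears only as background from other trials ("No evidence of disease activity (NEDA) was present in 48% of patients at 96 weeks"), and the studies of patients leaving natalizumab are cited mainly by relapse rate, which the primary endpoint matches. Much of this stands. A reader might infer that the plan committed itself to such a composite, or that a relapse-only primary endpoint is a mistake. The documents support neither.

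Three other inferences also go too far:

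- **That the relapse-free proportion must be at least as favourable as the joint figure.** This is true within one common patient set. Step 3 of the working shows that it can fail across the planned sets.
- **That the planned tables leave exactly the 55% to 80% range.** Two of its three inputs are assumed, and the EDSS proportion is not a planned output. The lower end also requires that no patient fails on two components. Some overlap is likely, because a protocol relapse needs objective EDSS or functional-system worsening, although that may recover by month 12. With positively associated components, roughly 61% to 80% is more plausible.
- **That the information is lost.** Relapse and EDSS are scheduled at months 3, 6, 9 and 12 and MRI at months 3, 6 and 12. A composite could be derived later from patient-level data; what is lost is prespecification.

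It can also be said that collection is incomplete for early leavers, because the premature termination visit in section 4.5.1 and Appendix A has no MRI. That is correct, and the fix has to allow for it. None of this answers the narrower point that section 4.9.3 discards MRI and EDSS data from patients who stop, while section 4.9.1 counts such patients for efficacy.

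**Conclusion.** The point holds as a gap between a three-part objective and the analyses meant to serve it. MRI and EDSS activity in patients who stop is excluded, relapse is analysed in a different set, and the proportion free of all three cannot be recovered from the planned results. A trivial exception would arise if no non-discontinuer relapsed and the reported range of EDSS change showed no worsening.

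The primary analysis, the sample size and each listed endpoint stand. The size is illustrative only: a 25-point range (55% to 80%) under the assumed 85% and 90% in one common set, and 29 points (0.60 to 0.89) in the assumed mixed-set example. This is an improvement worth making because it is cheap, not a correction of an invalid result.

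**What to change.** In sections 3.3.2 and 4.9.3, add one secondary endpoint: the proportion of all dosed patients in the full analysis set with no protocol-defined relapse, no new or enlarging T2 or new Gd+ lesion on any post-baseline scan, and no EDSS worsening, from baseline to month 12.

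- **EDSS rule.** Write the threshold into the plan before data are analysed, for example the half-step increase already used in the relapse definition, with a larger threshold as a sensitivity analysis. State that worsening first seen at month 12 is unconfirmed, since no later EDSS is scheduled.
- **Patients who stop.** Include their MRI and EDSS data, reconcile section 4.9.3 with section 4.9.1, and say whether discontinuing refers to ocrelizumab or to the study. Any positive component counts as active even if later data are missing.
- **Incomplete patients.** Show those with no positive component and incomplete data under best-case and worst-case counts, each with an exact 95% interval.

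The cost is analysis wording, one more secondary endpoint, and a figure that in the same set can be no more favourable than relapse-free alone and will usually be less so. At the planned 10% attrition, the best-case and worst-case results could differ by up to about 5/50, or 10 points, because early leavers have no termination MRI; completers with missed assessments would add to this.
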